7.6 FURTHER ENDPOINT(S)

Further endpoints are listed in CTP section 5.1.3.

7.6.1 Categorical endpoints

Categorical endpoints representing proportion of patients (as defined in [Section 5.3.2](#)) will be summarised descriptively. Wilson 95% confidence interval and a nominal p-value will be calculated for each proportion of patients specified in Section 5.3.2.

The proportion of patients with an absolute change from baseline in SGRQ \geq 4 points at week 52 will be analysed similarly.

The proportion of patients showing improvement based on CRISS will be summarised (improvement is defined based on CRISS value at 52 weeks and using a broad range of cut-offs) ([18]).

7.6.2 Change from baseline endpoints

Change from baseline endpoints at Week 52 (as defined in [Section 5.3.1](#)) will be summarised descriptively.

7.6.3 Analyses over the whole trial

Descriptive statistics by visit over the whole trial will be provided in the TS for endpoints listed in [Table 6.1: 1](#). A graphical representation of the change from baseline over the whole trial may also be displayed.

In addition, for exploratory purposes, a similar analysis as the primary model on the primary endpoint will be done, based on all data collected during the whole trial period (up to 100 weeks). Only the treatment effect and associated confidence interval will be provided.

7.6.4 Pharmacokinetics

For PK analyses, data will be summarised descriptively according to the BI Standard procedures ([6](#)).

7.6.5 Biomarkers

Analyses on biomarkers will be described in a separate Statistical Analysis Plan and not included in the main CTR.

7.7 EXTENT OF EXPOSURE

Extent of exposure data will be summarised on the TS both over 52 weeks and over the whole trial (refer to [Section 5.4.3.1](#) and [Section 5.4.3.2](#)).

A summary table showing the duration on treatment (both mean and frequency in classes, see [Section 5.4.3](#)) and dose intensity will be presented.

Besides, a summary table showing the duration on actual treatment dose (both mean and frequency in classes, see Section 5.4.3) and off-treatment duration will be performed. This will take into account the actual dose following dose reductions or increases.

A summary of treatment interruptions will be performed including number of patients with at least one interruption, number and reason of interruptions, as well as time to first interruption (both mean and frequency in classes, see Section 5.4.3). A similar summary will be performed for dose changes.

A table displaying the disposition of patients and the conclusion of patients' participation, and a table displaying the primary reason for non-inclusion/randomisation will be provided.

A Kaplan-Meier plot of time to premature treatment discontinuation will be produced. Similarly, Kaplan-Meier plots will be performed for time to first dose reduction and for time to first treatment interruption. No statistical tests will be performed.

7.8 SAFETY ANALYSIS

All safety analyses will be performed on the TS.

Safety analysis will primarily be based on data collected within the first 52 weeks. Additional safety analysis will also be presented for safety data collected overall including data collected beyond 52 weeks. See [Section 6.1](#) of this document for further details of the treatment period specifications and refer to [Table 6.1: 1](#) for the start and end dates for these analyses.

7.8.1 Adverse events

Unless otherwise specified, the analyses of adverse events will be descriptive in nature. All analyses of adverse events (AEs) will be based on the number of patients with AEs and NOT on the number of AEs (with the exception of AEs with additional information collection, see [Section 7.8.1.3](#)).

For analysis multiple AE occurrence data on the CRF will be collapsed into an AE event provided that all of the following applies:

- All AE attributes are identical (LLT, intensity, action taken, therapy required, seriousness, reason for seriousness, relationship [investigator defined drug-relatedness], outcome, AE of special interest)

- The occurrences were time-overlapping or time-adjacent (time-adjacency of 2 occurrences is given if the second occurrence started on the same day or on the day after the end of the first occurrence)

For further details on summarization of AE data, please refer to [\(8, 10\)](#).

The analysis of adverse events will be based on the concept of treatment emergent adverse events. That means that all adverse events occurring between first drug intake until last drug intake + 28 days will be assigned to the randomised treatment.

In addition, selected adverse events analyses will also be done considering a residual effect period of 7 days.

All adverse events occurring before first drug intake will be assigned either to ‘screening’ or ‘post-randomisation’ (for listings only).

For analyses based on a residual effect period of 28 days, adverse events occurring after last drug intake + 28 days will be assigned to ‘follow-up’ or ‘post-study’ (for listings only). All adverse events occurring between the start of an interruption of trial medication and the end of interruption of trial medication will be assigned to ‘off-treatment’ period in the listings. For details on the treatment definition, see [Section 6.1](#).

According to ICH E3 [\(11\)](#), AEs classified as ‘other significant’ need to be reported and will include those non-serious and non-significant (i.e. not defined as protocol-specified AEs of special interest) adverse events with

- (i) ‘action taken = discontinuation’ or ‘action taken = reduced’, or
- (ii) marked haematological and other lab abnormalities or lead to significant concomitant therapy

Adverse events related to gastrointestinal perforation and hepatic injury will be considered as protocol pre-specified AEs of special interest (AESIs), and were collected as such in the eCRF.

An overall summary of adverse events will be presented.

The frequency of patients with AEs will be summarised by treatment, primary system organ class (SOC) and preferred term (PT). This will also be presented restricted to incidence in preferred term > 5% (in at least one treatment arm).

Separate tables will be provided for patients with other significant AEs according to ICH E3 [\(11\)](#), for patients with serious AEs (SAEs), for patients with severe AEs, for patients with AEs leading to permanent dose reduction, for patients with AEs leading to permanent drug discontinuation, for patients with investigator defined drug-related AEs and for patients with AEs leading to death. The frequency of patients with SAEs will also be presented restricted to incidence in preferred term > 1% (in at least one treatment arm).

In addition a table will be provided for patients with investigator defined drug-related SAEs. This will be based on the number of patients with AE that are both serious and investigator

defined drug-related. Similarly, a table will be provided for patients with investigator defined drug-related AEs leading to deaths.

The SOCs and PTs (within SOCs) will be sorted by descending frequency in Nintedanib treatment arm.

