IRT call/notification	X	14	X		X		X		X		X		X		X	(X)	
Dispense trial medication			X		X		X		X		X		X		X		
Collect trial medication					X		X		X		X		X		X	X	
Compliance/drug accountability				X^{20}	X	X^{20}	X		X		X		X		X	X	
Physician global VAS			X						X				X			X	
Termination of trial medication ¹⁵																X	
Vital status assessment ¹⁶													X		·	X	
Conclude subject participation ¹⁷																	X

Footnotes:

* In case of dose change (reduction or re-escalation) additional visits have to be included (refer to Section 6.2.4).

- In case of prematurely trial medication discontinuation, the patient completes end of treatment Visit (EOT and follow-up Visit (FU) 4 weeks later), the patient should be asked to come to future visits as planned (refer to Section 6.2.3).
- EOT assessments are the same as described for Visit 12. If EOT is performed at week 52, the Flowchart for Visit 9 is valid (i.e. Biomarker samples to be drawn).

Before or at the latest at Visit 1. Informed consent (IC) needs to be signed before any procedure related to the trial is performed. All adverse events (AEs) and concomitant therapies (CTs) from the day of signing informed consent have to be recorded. The screening period (informed consent to Visit 2) must not be longer than 12 weeks.

² Review of high resolution computer tomography (HRCT) for extent of fibrotic disease in the lung (10% or more). Central review: a historical HRCT not older than 12 months should be sent; only if the patient does not have a HRCT within 12 months at Visit 1 but meets all other inclusion and no exclusion criteria, the HRCT can be performed for the purposes of participation in the trial (except for patients in Germany).

c03014699-05 Trial Protocol Proprietary confidential information © 2018 Boehringer Ingelheim International GmbH or one or more of its affiliated companies

³ Self-reported outcome questionnaires must always be done by the patients in a quiet place prior to any other visit procedure. Order of questionnaires: 1. SGRQ, 2. FACIT-dyspnoea, 3. SHAQ, 4. EQ-5D-5L, 5. Patient's global VAS.

⁴ The safety lab of Visit 1 must be repeated if screening is longer than 6 weeks.

⁵ Intermediate lab tests (a-Visit) do not necessarily need to be a site visit. Cautionary note: dependent on concomitant treatment additional safety monitoring should be considered at discretion of the investigator.

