5.3.8 Adverse event collection and reporting

The following must be collected and documented on the appropriate eCRF by the Investigator:

From signing the informed consent through to the end of the residual effect period (REP) of at least 28 days after the date of last dose, all AEs (serious and non-serious) will be collected. If a patient discontinues trial medication but continues to attend future visits, all AEs (serious and non-serious) should be collected until the patient completes the trial. AEs starting on or after the date of first dose of trial medication, and up to 28 days after the date of last dose will be considered as on-treatment.

After the individual patient's end of trial the investigator does not need to actively monitor the patient for AEs but should only report relevant SAEs and relevant AESIs of which the investigator may become aware of.

AE reporting to sponsor and timelines

The Investigator must report SAEs, and non-serious AEs which are relevant for the reported SAE on the BI SAE form via fax immediately (within 24 hours) to the Sponsor's unique entry point (country specific contact details will be provided in the ISF). The same timeline applies if follow-up information becomes available. In specific occasions the Investigator could inform the Sponsor upfront via telephone. This does not replace the requirement to complete and fax the BI SAE form.

For Japan:

All SAEs and AESIs must be reported immediately to the head of the trial site.

With receipt of any further information to these events, a follow-up SAE form has to be provided. For follow-up information the same rules and timeline apply as for initial information.

Information required

For each AE, the Investigator should provide the information requested on the appropriate eCRF pages and the BI SAE form (if applicable), e.g. onset, end date, intensity, treatment required, outcome, seriousness, and action taken with the investigational drug(s). The Investigator should determine the causal relationship to the trial medication and the trial procedures outlined under Section 6.2.

The following should also be recorded as an (S)AE in the eCRF and SAE form (if applicable):

- Worsening of the underlying disease or of other pre-existing conditions
- Changes in vital signs, ECG, physical examination and laboratory test results, if they are judged clinically relevant by the Investigator.

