7.3.4 Safety analyses

Adverse events will be coded using the Medical Dictionary for Regulatory Activities (MedDRA) coding dictionary. Standard BI summary tables and listings will be produced. All treated patients will be included in the safety analysis. In general, safety analyses will be descriptive in nature and will be based on BI standards. No hypothesis testing is planned.

Statistical analysis and reporting of adverse events will concentrate on treatment-emergent adverse events. To this end, all adverse events occurring between start of treatment and end of the residual effect period will be considered 'treatment-emergent'. The residual effect period is the 28 days after the date of the last dose of trial medication. Adverse events that start before first drug intake and deteriorate under treatment will also be considered as 'treatment-emergent'. Based on the half-life of the study drug, adverse events that occur between the start of treatment and up to 7 days after the date of the last dose of trial medication will be analysed in addition.

Frequency, severity, and causal relationship of adverse events will be tabulated by system organ class and preferred term after coding according to the current version of the MedDRA.

Laboratory data will be analysed both quantitatively as well as qualitatively. The latter will be done via comparison of laboratory data to their reference ranges. Values outside the reference range as well as values defined as clinically relevant will be highlighted in the

Proprietary confidential information © 2018 Boehringer Ingelheim International GmbH or one or more of its affiliated companies

listings. Treatment groups will be compared descriptively with regard to distribution parameters as well as with regard to frequency and percentage of patients with abnormal values or clinically relevant abnormal values.

Vital signs, physical examinations, or other safety-relevant data observed at screening, baseline, during the course of the trial and at the end-of-trial evaluation will be assessed with regard to possible changes compared to findings before start of treatment.

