3. INTRODUCTION

As per ICH E9 (3), the purpose of this document is to provide a more technical and detailed elaboration of the principal features of the analysis described in the protocol, and to include detailed procedures for executing the statistical analysis of the primary and secondary variables and other data.

This TSAP assumes familiarity with the Clinical Trial Protocol (CTP), including Protocol Amendments. In particular, the TSAP is based on the planned analysis specification as written in CTP Section 7 “Statistical Methods and Determination of Sample Size”. Therefore, TSAP readers may consult the CTP for more background information on the study, e.g., on study objectives, study design and population, treatments, definition of measurements and variables, planning of sample size, randomisation.

SAS® Version 9.4 or later will be used for all analyses.

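### SAP 7.8.1 sends every pre-dose adverse event to listings only, which conflicts with the Protocol 7.3.4 rule that those deteriorating under treatment are treatment-emergent

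*SAP*

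**What the plan says.** Protocol 7.3.4 gives two routes to treatment-emergent status. The first is a window: "all adverse events occurring between start of treatment and end of the residual effect period will be considered" treatment-emergent, with a residual effect period of 28 days after the last dose. The second concerns earlier onset: "Adverse events that start before first drug intake and deteriorate under treatment will also be considered as" treatment-emergent.

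SAP 7.8.1 says that its AE analysis rests on the treatment-emergent concept, and explains the concept by the window only: "all adverse events occurring between first drug intake until last drug intake + 28 days will be assigned to the randomised treatment". It then says that "All adverse events occurring before first drug intake will be assigned either to" screening or post-randomisation, and marks both categories as being for listings only. It makes no exception for an event that later worsens.

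SAP Table 6.1: 1 also starts the on-treatment safety analyses at first drug intake. SAP Section 4, which lists departures from the protocol analysis, does not mention AEs.

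**The concern.** The two documents classify the same event differently. An AE that begins in screening and becomes worse after the first dose is treatment-emergent under the protocol. Read literally, the SAP keeps it out of every AE frequency table.

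Such events can be expected to exist. AEs are collected from consent (Protocol 5.3.8), and the flowchart footnote says: "The screening period (informed consent to Visit 2) must not be longer than 12 weeks". Medication washout takes place after consent and within that period (Protocol 6.2.1).

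At stake is the descriptive safety comparison, possibly in the drug's main tolerability area. Protocol 1.2 names diarrhoea as the most frequently reported AE with nintedanib, and SAP 7.8.1.5 treats gastrointestinal AEs as being of particular note. If worsening of screening-onset AEs is more frequent on nintedanib, leaving them out makes the arms look more alike than they are.

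**Working it through.** The documents give no figure for this point, so the check compares the texts.

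**1. The two definitions**

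| Event | Protocol 7.3.4 | SAP 7.8.1 |
|---|---|---|
| Starts between first dose and 28 days after last dose | Treatment-emergent | Treatment-emergent |
| Starts before first dose, does not deteriorate under treatment | Not treatment-emergent | Listings only |
| Starts before first dose, deteriorates under treatment | Treatment-emergent | Listings only |

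The documents disagree in the third row only.

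**2. Is the clause elsewhere in the SAP?** I did not find it. SAP 7.8.5 has worsening of SSc-ILD summarised as an AE, but that covers the trial indication only. SAP 7.8.1.6, for the whole trial, works from first onset and does not mention deterioration.

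**3. Which events are at risk?** An event has to pass through each of these steps:
- It starts after consent and before the first dose. Conditions already present at trial inclusion are baseline conditions (Protocol 5.3.8), and their worsening is to be recorded as an AE (Protocol 5.3.1 and 5.3.8).
- It deteriorates under treatment.
- It stays as one record with its pre-dose start date. If the site enters a new, more intense occurrence, SAP 7.8.1 does not collapse it into the earlier one, because collapsing requires identical attributes, including intensity. The new occurrence starts after first intake and is counted.

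The collapsing rule deals with occurrences that have already been entered. It does not tell sites to open a new record when a screening-onset AE worsens. The recording rules on worsening concern pre-existing and baseline conditions, so this group is not clearly covered.

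**4. What size would depend on.** Let p be the proportion of patients with an AE that starts in the pre-dose period and is still present at first dose. Randomisation makes p about equal in the two arms. Let w_N and w_P be the proportions of these patients whose AE worsens under nintedanib and placebo. Let s be the share of worsened AEs that are held as one pre-dose record in a patient with no other counted occurrence of the same term, taken as equal in both arms. The understatement of the between-arm difference for that term is then

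p × s × (w_N − w_P).

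The documents give none of these quantities. If s = 0 the effect is nil. If w_N = w_P, counts fall in both arms but the difference does not change.

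**The case against.** The strongest reply is that nothing was removed. The SAP introduction assumes familiarity with the protocol and says that "the TSAP is based on the planned analysis specification as written in CTP Section 7", which is where the worsening clause sits. On this reading SAP 7.8.1 is an incomplete restatement, and Section 4 had nothing to declare. That is plausible as to intent. It does not settle the matter, because a general introduction does not override a specific sentence that covers all pre-dose AEs. Where the SAP relies on protocol text it tends to say so: SAP 7.8.2 refers to Protocol 7.3.4 for laboratory data, but the AE section has no such reference.

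A second reply is that the harm needs a particular way of recording, and that the SAP's provision for several occurrences of one AE points towards separate entries. This stands as a limit on the consequence, though neither document requires separate entries for screening-onset AEs.

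A third reply also stands in large part. A reader might infer that worsening of the gastrointestinal symptoms that SSc patients already have (Protocol 2.3) would be lost. The documents do not support that: Protocol 5.3.8 lists "Worsening of the underlying disease or of other pre-existing conditions" among the things to be recorded as an AE. Only AEs that begin between consent and first dose are exposed.

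Finally, SAP 7.8.1 refers to sponsor standards for further details of AE summarisation. These might contain a worsening rule, but their content is not in the documents. Safety analyses are descriptive with no hypothesis testing (Protocol 7.3.4), so no confirmatory result is affected.

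**Conclusion.** The SAP sentence is wrong as written. It conflicts with a stated protocol rule, and the difference is not declared in SAP Section 4.

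The consequence is conditional. It arises only for AEs that start between consent and first dose, deteriorate under treatment, and are kept as one record with the pre-dose date. The between-arm difference is understated only if such worsening is more frequent on nintedanib.

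A reader might infer a definite bias of known size. For example, assume that p = 10%, w_N = 40%, w_P = 15% and s = 1; the formula then gives 0.10 × 1 × (0.40 − 0.15) = 2.5 percentage points. The documents support none of these inputs, and the assumed contrast produces the answer. Setting s = 1 also makes it an upper illustration: SAP 7.8.1 counts patients, not events, so a patient with another on-treatment occurrence of the same term is counted anyway. The size should be left as not derivable, with nil as a possible value.

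**What to change.** In SAP 7.8.1:
- Restate the Protocol 7.3.4 clause on AEs that start before first intake and deteriorate under treatment.
- Limit the listings-only sentence to pre-dose AEs that do not deteriorate under treatment.
- State how deterioration is identified in the data, for example by an on-treatment record with higher intensity.

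The protocol clause says only that the event deteriorates under treatment. Extra criteria, such as a change to serious, worsening during the residual effect period, or a reset onset date, would be additions to it and should be labelled as such if the sponsor wants them. If the narrower SAP definition is in fact intended, it should be declared in SAP Section 4 with a reason.

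The cost is one or two sentences and one derivation step. Some AE frequencies may become slightly higher. If sites already record worsening as separate occurrences, no count changes and the contradiction is removed.

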5.3.7 Assessment of adverse events

5.3.7.1 Definitions of AEs

Adverse event

An adverse event (AE) is defined as any untoward medical occurrence in a patient or clinical investigation subject administered a medicinal product and which does not necessarily has to have a causal relationship with this treatment.

An AE can therefore be any unfavourable and unintended sign (including an abnormal laboratory finding), symptom, or disease temporally associated with the use of a medicinal product, whether or not considered related to the medicinal product.

Serious adverse event

A serious adverse event (SAE) is defined as any AE which:

- Results in death,
- Is life-threatening,
- Requires inpatient hospitalisation or prolongation of existing hospitalisation,
- Results in persistent or significant disability or incapacity,
- Is a congenital anomaly/birth defect
- Is to be deemed serious for any other reason if it is an important medical event when based upon appropriate medical judgment which may jeopardize the patient and may require medical or surgical intervention to prevent one of the other outcomes listed in the above definitions.

Proprietary confidential information © 2018 Boehringer Ingelheim International GmbH or one or more of its affiliated companies

Life-threatening in this context refers to an event in which the patient was at risk of death at the time of the event; it does not refer to an event that hypothetically might have caused death if more severe.

Every new occurrence of cancer must be reported as a serious event regardless of the duration between discontinuation of the drug and the occurrence of the cancer.

For Japan, the following events will be handled as "deemed serious for any other reason". An AE which possibly leads to disability will be reported as an SAE:

AEs considered "always serious"

In accordance with the European Medicines Agency initiative on Important Medical Events, Boehringer Ingelheim has set up a list of AEs, which by their nature, can always be considered to be "serious" even though they may not have met the criteria of an SAE as given above.

The latest list of "always serious AEs" can be found in the Remote Data Capture (RDC) system (list of implied serious adverse events). These events should always be reported as SAEs as described in Section 5.3.7.

Adverse events of special interest (AESIs)

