5.2.2.2 Time to death

Time to death (over the whole trial duration, including after 52 weeks) is defined with start date being the date of randomisation. Patients who did not die during the trial will be censored at the last contact date.

For this endpoint, the last contact date of a patient is defined as the latest date recorded in the Case Report Form (CRF) from the dates listed below:

Date of last visit, last reported Adverse Event (AE) (excluding censored dates), last reported concomitant treatment date, last laboratory sample date, last drug intake, last reported date in menstruation diary, last reported dose change / interruption date, date of trial completion, last known alive date or date of death.

Refer to [Table 6.1:1](#) for details of the analysis periods used for time-to-event endpoints.

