Safety survival analysis over 52 weeks ^[2]	Time to - first dose reduction - first treatment interruption - premature treatment discontinuation	Date of first trial drug intake	- If last drug intake < Day 373: Last drug intake - Else, if last drug intake ≥ Day 373: Day 373
On-treatment safety analyses over 52 weeks	- Adverse events - Laboratory data - Vital signs	Date of first trial drug intake	- If last drug intake < Day 373: Last drug intake + 28 days - Else, if last drug intake ≥ Day 373: Day 373
On-treatment safety analyses (over the whole trial)	- Adverse events - Laboratory data - Vital signs	Date of first trial drug intake	Last trial drug intake + 28 days Off-treatment periods not excluded. However, for safety listings, anything happening during a treatment interruption will be flagged as occurring during the off-treatment period

[1] End date is included. End date will always be checked against the date of first trial drug intake in 1199.225. For safety endpoints, if date of first trial drug intake in 1199.225 is earlier than end date calculated as mentioned in this table, then the end date of the studied period will be substituted by the date of first trial drug intake in 1199.225

[2] For time-to-event endpoint, if a patient does not have an event during the studied period then ■ will be censored on the day corresponding to the end date of the studied period

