7.8.1.3 Adjudicated adverse events

An independent adjudication committee will review all fatal cases and adjudicate cause of death to cardiovascular death, respiratory related death, non-cardiovascular/non-respiratory death, or undetermined cause of death on a per patient basis, e.g. one cause per patient. The adjudication committee will also review all AEs categorised as MACE according to the definition in the adjudication charter.

In addition to standard safety analyses, the frequency of patients with AEs leading to death will be summarised by treatment, adjudicated cause of death (Cardiac, Respiratory, Non-cardiac/non-respiratory or Undetermined), and PT.

The frequency of patients with AEs categorised as MACE (that is all AEs with trigger terms for MACE and therefore sent for adjudication) will be summarised by treatment and outcome of adjudication (adjudicated as MACE or adjudicated as not MACE). The frequency of patients with AEs adjudicated as MACE will also be summarised by treatment and PT.

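### Adjudicated causes of death and MACE arising more than 28 days after the last dose have no comparative table, and the 52-week safety window is not capped at Day 373

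*SAP*

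**What the plan says.** **Late events.** SAP 7.8.1 builds its AE analysis on treatment-emergent events: "all adverse events occurring between first drug intake until last drug intake + 28 days will be assigned to the randomised treatment". Where the 28-day residual period applies, "adverse events occurring after last drug intake + 28 days will be assigned to" the follow-up or post-study period, which is used for listings only. SAP 7.8 refers to Table 6.1:1 for start and end dates, and there the whole-trial safety window also ends at last intake plus 28 days.

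For adjudicated events, SAP 7.8.1.3 says that "the frequency of patients with AEs leading to death will be summarised by treatment, adjudicated cause of death" and preferred term, and it plans MACE tables. SAP 7.8.1.6 repeats these over the whole trial on a time-at-risk basis. Neither section names a window of its own.

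Collection and the mortality endpoint reach further. Protocol 5.3.8 says that for patients who stop drug but keep attending, "all AEs (serious and non-serious) should be collected until the patient completes the trial". The adjudication committee reviews all fatal cases and all events categorised as MACE. SAP 5.2.2.2 defines "Time to death (over the whole trial duration, including after 52 weeks") from randomisation, with survivors censored at last contact.

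**The 52-week window.** SAP 7.8 states that "Safety analysis will primarily be based on data collected within the first 52 weeks". Table 6.1:1 gives the end date for AEs, laboratory data and vital signs over 52 weeks as: "If last drug intake < Day 373: Last drug intake + 28 days - Else, if last drug intake ≥ Day 373: Day 373".

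**The concern.** The table meant to explain the deaths by cause can cover fewer deaths than the mortality endpoint beside it. The deaths without a tabulated cause are those whose fatal AE began more than 28 days after the last dose. Late MACE drop out in the same way. Whether an event is dropped depends on having stopped drug, which happens after randomisation and may differ between arms. A comparison by randomised arm using all follow-up would not have this weakness, and the data for it are already being collected and adjudicated.

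The second matter is one of consistency. A table labelled 52 weeks should stop at the SAP's own Week 52 cut for everyone. As written, a patient with last intake on Day 372 contributes to Day 400, and one with last intake on Day 373 contributes to Day 373.

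**Working it through.** **(a) Events more than 28 days after the last dose**

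| Item | Runs to | Source |
|---|---|---|
| AE tables, including whole trial | last intake + 28 days | SAP 7.8.1, Table 6.1:1 |
| Adjudicated cause of death, MACE | no window given, so as above | SAP 7.8.1.3, 7.8.1.6 |
| AE collection after stopping drug | trial completion | Protocol 5.3.8 |
| Time to death | last contact | SAP 5.2.2.2, Table 6.1:1 |

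For a patient with last intake on day L who is followed to day F, the follow-up outside every AE table is F − (L + 28) days. To the Week 52 cut (F = 373):

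- L = 90: 373 − 118 = 255 days
- L = 180: 373 − 208 = 165 days
- L = 270: 373 − 298 = 75 days

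The documents give no discontinuation rate, so any trial-level figure rests on assumptions. Take uniform entry over 78 weeks (Protocol 3.3 expects about 18 months) and last visits at weeks 52, 68, 84 and 100. The shares are then 16/78, 16/78, 16/78 and 30/78, and mean planned follow-up is 1.54 years. With a fraction p stopping per year, λ = −ln(1 − p), planned time T and c = T − 28/365.25, the expected time beyond 28 days off drug is c − (1 − e^(−λc))/λ.

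| p per year | Years at T = 52, 68, 84, 100 weeks | Weighted mean | Share of 1.54 | Per 260 patients |
|---|---|---|---|---|
| 10% | 0.043, 0.076, 0.117, 0.167 | 0.113 | about 7% | about 29 patient-years |
| 20% | 0.088, 0.154, 0.235, 0.331 | 0.225 | about 15% | about 59 patient-years |

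These are upper figures for AE data, because they follow every discontinuer to the planned end. They describe follow-up time; they do not estimate how many deaths or MACE are missed.

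**(b) The 52-week end date**

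The plan's own cut reproduces: Day 1 + 372 = Day 373 (SAP 6.7). The flowchart puts Visit 9 at Day 365 ± 7, that is Day 358 to 372. All of these are below 373, so an end-of-treatment visit (EOT) that replaces Visit 9 on schedule always takes the branch that adds 28 days (taking last intake to be on the visit day).

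| Last intake | End under Table 6.1:1 | Days past 373 |
|---|---|---|
| Day 345 | Day 373 | 0 |
| Day 346 | Day 374 | 1 |
| Day 358 | Day 386 | 13 |
| Day 365 | Day 393 | 20 |
| Day 372 | Day 400 | 27 |
| Day 373 or later | Day 373 | 0 |

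Premature stops on Day 346 to 372 overrun too. A footnote to the table ends the safety window at the first dose in the extension trial if that comes earlier, so these are upper limits for patients who roll over.

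Elsewhere the SAP stops at Day 373: exposure (5.4.3.1), safety time-to-event over 52 weeks (5.4.6) and concomitant therapy (7.2.2). Table 6.7:3 allocates laboratory values from Day 374 to the Week 60 visit, although Table 6.1:1 would count some of them in the 52-week analysis.

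Size: those randomised in the last 16 weeks (112 days) end at Visit 9. With uniform accrual over 18 months the share is 112/(18 × 30.44) = 20.4%, or about 106 of 520. At 20 extra days each this is 106 × 20/365.25 = 5.8 patient-years, about 1% of 520 × 373/365.25 = 531. Accrual over 24 or 12 months would give 15% or 31% of patients and 4.4 or 8.7 patient-years.

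**The case against.** The strongest reply on (a) has four parts.

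- **Late deaths are not lost.** A reader might infer that they are. They are compared by arm in time to death, by Cox model and Kaplan-Meier plot, or as numbers and percentages if deaths are under 2% (Protocol 7.3.2.2). This stands: only the adjudicated cause lacks a comparison.
- **The 28-day focus is the protocol's own.** Protocol 7.3.4 says that AE reporting will concentrate on treatment-emergent events and defines the same period. This stands too: the SAP does not depart from the protocol, and the 28-day tables are legitimate.
- **The exclusion is inferred.** SAP 7.8.1.3 sets no window and speaks of all fatal cases. That is fair, but 7.8, 7.8.1 and Table 6.1:1 supply the default and nothing overrides it. If a wider window is intended, the SAP should say so.
- **The whole-trial tables use rates.** Under SAP 7.8.1.6, if time at risk ends with the window, off-drug person-time leaves along with the events. That would reduce distortion of the rates, but it does not supply the missing causes.

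It is also tempting to conclude that the omission favours nintedanib, because its gastrointestinal and hepatic toxicity leads to discontinuation. That needs more stopping in the nintedanib arm and a particular risk of death off drug. The documents give neither figure.

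A cancer table does not follow either. Protocol 5.3.7.1 says that a new cancer "must be reported as a serious event regardless of the duration between discontinuation of the drug and the occurrence of the cancer", but this is a reporting rule, and Table 7.8.1.4:1 has no cancer topic.

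On (b), the reply is that the overrun is small and, for patients ending at Visit 9, is set by date of randomisation, so it should balance between arms. This stands. A reader might also infer that the overrun brings in the off-drug follow-up visit. That visit is planned 28 to 35 days after last intake, so it falls inside the window only if held exactly on day 28.

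**Conclusion.** Both parts hold in limited form.

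(a) On a plain reading, adjudicated cause of death and MACE with onset more than 28 days after last intake appear in listings only, although they are collected and adjudicated. The cause-of-death table can therefore cover fewer deaths than time to death. A fatal AE that began within 28 days still counts, even if death came later. The number of events affected and the direction of any imbalance cannot be derived from the documents. The 7% to 15% of follow-up shown above rests on assumed discontinuation of 10% to 20% per year.

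(b) The 52-week safety end date is inconsistent with the Day 373 cut used elsewhere. The overrun is 1 to 27 days for last intake on Day 346 to 372, and at most about 6 patient-years for patients ending at Visit 9. That figure assumes uniform 18-month accrual, Visit 9 on its nominal day and no early start of extension drug. It does not undermine the 52-week safety comparison.

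**What to change.** **SAP 7.8.1.3 and 7.8.1.6:** add tables of adjudicated cause of death and of adjudicated MACE by randomised arm, from first intake to last contact as defined for time to death. Keep the 28-day tables and label them as the on-treatment analysis.

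**SAP Table 6.1:1:** for on-treatment safety analyses over 52 weeks, set the end date to the earlier of last intake plus 28 days and Day 373, keeping the existing rule on the first extension-trial dose.

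The cost is SAP wording and a few extra tables, with no new data and no further adjudication. The limitation to state is that AE collection is incomplete in patients who refuse further visits: their vital status is sought, but late non-fatal MACE may be missed.
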